7 DISCONTINUATION OF STUDY INTERVENTION AND PATIENT DISCONTINUATION/WITHDRAWAL

7.1 Discontinuation of study intervention

Patients may be discontinued from IP in the following situations. Note that discontinuation from study treatment is NOT the same thing as a complete withdrawal from the study.

- Patient decision. The patient is at any time free to discontinue treatment, without prejudice to further treatment.
- Adverse events.
- Severe non-compliance with the Clinical Study Protocol.
- Objective disease progression as per RECIST 1.1. Patients may continue to receive treatment with osimertinib + savolitinib beyond RECIST 1.1-defined progression as long as they continue to receive clinical benefit, in the opinion of the investigator, and do not meet any of the discontinuation criteria.
- Patients incorrectly initiated on study medication.
- Pregnancy.
- Specific stopping criteria ie, ILD, acute anaphylaxis or QTcF interval prolongation with signs/symptoms of serious arrhythmia.

See the SoA ([Table 1](#) and [Table 2](#)) for data to be collected at the time of treatment discontinuation and follow-up and for any further evaluations that need to be completed.

Continuing on monotherapy

A patient can continue on savolitinib monotherapy (if osimertinib was stopped earlier or if randomised to the savolitinib plus placebo arm) until objective disease progression.

Savolitinib monotherapy beyond RECIST 1.1 progression is not permitted.

A patient who is originally randomised to savolitinib + osimertinib arm may continue to receive treatment with osimertinib monotherapy (if savolitinib was stopped earlier) beyond RECIST 1.1-defined progression as long as they continue to receive clinical benefit, in the opinion of the principal investigator and do not meet any of the discontinuation criteria (this may be beyond disease progression in the absence of clinical symptoms or signs indicating clinically significant disease progression; no decline in performance status; absence of rapid disease progression or threat to vital organs or critical anatomical sites [eg, central nervous system metastasis, respiratory failure due to tumour compression, spinal cord compression] requiring urgent alternative medical intervention; or no significant, unacceptable or irreversible toxicities related to study treatment), according to the SoA ([Table 1](#)).

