- c The frequency of liver function tests will depend on the timepoint at which the patient crosses over. Liver function tests should be performed weekly for the first 10 weeks of the study (ie, for patients who cross over prior to completing 10 weeks of the study) then on Day 1 of every subsequent cycle in the crossover period. Where a liver function test is the only assessment, a clinic visit is not required as the test may be performed offsite. In the case of elevated liver function tests, please refer to Appendix I 3.3 for enhanced monitoring and management procedures.
- f At all visits, [REDACTED] mL blood for plasma is required for ctDNA to measure clearance of EGFR mutation alleles and for exploratory analysis.
- g **CCI** [REDACTED] for savolitinib and is optional.
- h For patients who cross over based on confirmed objective disease progression during the initial randomised treatment period, scheduled RECIST 1.1 tumour assessments are not required, and the subsequent assessment of disease progression will be based on standard-of-care scan or investigator determined clinical progression. Scheduled RECIST 1.1 tumour assessments are required (the scan frequency is against initial randomisation) for patients who cross over based on a declaration of futility of the savolitinib monotherapy arm and who have not objectively progressed during the initial randomised treatment period. Patients who cross over based on a declaration of futility, who have no objective progression during initial randomisation period, and who discontinue study drug after cross-over for reasons other than investigator-confirmed disease progression will continue scheduled RECIST 1.1 tumour assessments until objective disease progression per RECIST 1.1 as assessed by investigator, unless they withdraw consent to the entire study. At the same time points, vital signs, and ECGs will be collected. SAEs considered related to study treatment and/or study procedures will be collected throughout progression follow-up.
- i Patients who cross over must not receive any other anti-cancer therapies between the assessment of PD and the addition of osimertinib. Savolitinib treatment should continue uninterrupted during this period.

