- ^e Planned to include approximately **CCI** post 1L patients with MET amplification/overexpression (FISH10+ and/or IHC90+) under CSP version 7.0 to receive savolitinib 300 mg bid + osimertinib 80 mg.

1L First line; 2/3L Second/third line; CSP Clinical study protocol; NA Not applicable.

Under CSP version 7.0, patients must have central confirmation of MET amplification and/or overexpression (FISH10+ and/or IHC90+) by FISH and IHC (central) testing. Pre-existing next generation sequencing (NGS) testing results are not accepted to enter Screening.

Provision of a formalin fixed and paraffin embedded (FFPE) tumour sample is mandatory.

Approximately **CCI** freshly cut (within **CCI** days) unstained sections (**CCI** micron) from FFPE tissue blocks or FFPE blocks containing equivalent material will be required per patient (refer to Central Laboratory Manual for detailed tissue requirements). Samples **CCI** years old will not be accepted.

Patients determined to be MET-amplified and/or overexpressed by FISH and IHC in Pre-screening will undergo screening during the 28 days prior to first administration of study medication to confirm eligibility (Sections 5.1 and 5.2).

Patients will continue to receive study medication in 28-day cycles until objective disease progression, unacceptable toxicity occurs, consent is withdrawn or another discontinuation criterion is met (Section 7). Patients may continue to receive treatment with osimertinib + savolitinib or osimertinib monotherapy (if savolitinib was stopped earlier) beyond RECIST 1.1-defined progression as long as they continue to receive clinical benefit, in the opinion of the investigator, and do not meet any of the discontinuation criteria (this may be beyond disease progression in the absence of clinical symptoms or signs indicating clinically significant disease progression; no decline in performance status; absence of rapid disease progression or threat to vital organs or critical anatomical sites [eg, CNS metastasis, respiratory failure due to tumour compression, spinal cord compression] requiring urgent alternative medical intervention; or no significant, unacceptable or irreversible toxicities related to study treatment) (Section 7.1). Patients can continue on savolitinib monotherapy (if osimertinib was stopped earlier or if randomised to the savolitinib + placebo arm) until objective disease progression. Savolitinib monotherapy post progression is not permitted.

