4.1.2 Crossover

At investigator-assessed PD per RECIST 1.1, treatment allocation will be unblinded and those patients randomised to the savolitinib plus placebo arm will have the opportunity to cross over to the savolitinib plus osimertinib regimen. Patients will be informed of the possibility of crossover to savolitinib plus osimertinib during the initial informed consent process and at the

time of progression on randomised treatment. A separate informed consent form (ICF) for crossover patients must be signed prior to starting crossover treatment.

Patients who cross over must not receive any other anti-cancer therapies between the initial assessment of PD and the addition of osimertinib. Savolitinib treatment should continue uninterrupted during this period. Patients should be crossed over as soon as possible after the assessment of PD and within 28 days of their progression scan.

Patients who cross over will receive study medication once daily in 28-day cycles until objective PD by RECIST 1.1 is assessed by investigator, unacceptable toxicity occurs, consent is withdrawn or another discontinuation criterion is met. As in the treatment allocation/randomisation part of the study, patients may continue to receive treatment with osimertinib plus savolitinib or osimertinib monotherapy (if savolitinib is stopped during cross over because of savolitinib-related toxicity) beyond RECIST 1.1 defined PD as long as they continue to receive clinical benefit, in the opinion of the investigator, and do not meet any of the discontinuation criteria. No other anti-cancer agent is permitted in combination with osimertinib within this study.

If, after the planned futility analysis the savolitinib + placebo arm is declared futile, all patients remaining on savolitinib + placebo will be contacted and asked to return for a discussion of the futility findings and their options for remaining in the savolitinib + placebo arm (as long as, in the opinion of the investigator, they are still receiving clinical benefit and have not reported PD) or crossing over to the savolitinib + osimertinib arm. Patients who cross over must not receive any other intervening anti-cancer therapies before the addition of osimertinib.

All patients who cross over to receive savolitinib + osimertinib (whether based on objective PD by RECIST 1.1 or a declaration of futility of the savolitinib + placebo arm) will follow the scheduled procedures described in [Table 2](#).

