Patients randomised to the savolitinib 300 mg bid + placebo arm may cross over to savolitinib 300 mg bid plus osimertinib 80 mg od following investigator assessment of PD per RECIST 1.1. Once the investigator has documented progression in the eCRF, and obtained approval for unblinding from the study physician, the treatment code for a patient may be obtained from the IWRS via a dedicated option they may select in this situation. In all other circumstances the treatment code should not be unblinded except in medical emergencies when the appropriate management of the patient requires knowledge of the treatment allocation. The investigator documents and reports the action to the AstraZeneca study physician, without involvement of other personnel to maintain study integrity.

AstraZeneca retains the right to break the code for SAEs that are unexpected and are suspected to be causally related to an investigational product and that potentially require expedited reporting to regulatory authorities.

Treatment codes will not be unblinded for the planned analyses of data until all decisions on the evaluability of the data from each individual patient have been made and documented.

The IWRS will be programmed with blind-breaking instructions. In case of an emergency, in which the knowledge of the specific blinded study intervention will affect the immediate management of the patient's condition (eg, antidote available), the investigator has the sole responsibility for determining if unblinding of a patients' treatment assignment is warranted. Patient safety must always be the first consideration in making such a determination. If a patient's treatment assignment is unblinded, the sponsor must be notified within 24 hours after

breaking the blind. The investigator documents and reports the action to the AstraZeneca physician, without involvement of other personnel to maintain study integrity. Additionally, patients with investigator-assessed objective PD may be unblinded.

The personnel analysing the PK samples will be unblinded to the investigational treatment for each patient.

The AstraZeneca study team will be unblinded at the time of the primary analysis. Site staff and patients will remain blinded until database lock for the final analysis.

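### The ban on savolitinib monotherapy after progression (Protocol 4.1.1 and 7.1) makes no exception for crossover patients, whom Section 4.1.2 tells to keep taking savolitinib until osimertinib is added

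*Protocol*

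**What the plan says.** Two places in the protocol set a limit on savolitinib given alone.

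- Section 4.1.1: "Patients can continue on savolitinib monotherapy (if osimertinib was stopped earlier or if randomised to the savolitinib + placebo arm) until objective disease progression". It then adds: "Savolitinib monotherapy post progression is not permitted".
- Section 7.1, under the sub-heading on continuing with a single agent: "A patient can continue on savolitinib monotherapy (if osimertinib was stopped earlier or if randomised to the savolitinib plus placebo arm) until objective disease progression". It then adds: "Savolitinib monotherapy beyond RECIST 1.1 progression is not permitted".

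Two other places deal with patients who cross over from savolitinib + placebo to the combination.

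- Section 4.1.2 bars other anti-cancer treatment between PD and the start of osimertinib, and says of that interval: "Savolitinib treatment should continue uninterrupted during this period". It also sets the timing: "Patients should be crossed over as soon as possible after the assessment of PD and within 28 days of their progression scan".
- Table 2 footnote i (Section 1.1) repeats both instructions. It states: "Patients who cross over must not receive any other anti-cancer therapies between the assessment of PD and the addition of osimertinib". It then gives the same direction to keep savolitinib going.

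Section 6.3 describes how the site learns the treatment arm. The code can be obtained "Once the investigator has documented progression in the eCRF, and obtained approval for unblinding from the study physician".

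**The concern.** Section 7.1 is where a site looks to decide whether to stop a drug at progression. For a placebo-arm patient about to cross over, its answer is to stop savolitinib. Section 4.1.2 answers that savolitinib continues. The two rules cover the same patient on the same days.

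If the ban is followed, two things happen. First, savolitinib stops and nothing may replace it, because the crossover text forbids any other anti-cancer therapy in the interval. The patient has been without an EGFR inhibitor since randomisation, and Section 2.3.1 warns of rapid progression after EGFR-TKI withdrawal. Second, savolitinib has to be restarted at crossover. Appendix I 3.4 reports that acute hypersensitivity, including anaphylaxis, occurred mostly when savolitinib was restarted. The restart precautions there, and the rechallenge guidance in Section 7.1.1, are written for interruptions caused by toxicity or adverse events. Neither addresses a stop made because of progression.

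**Working it through.** The plan gives no figure to reproduce and no arithmetic applies. The check is a comparison of the rules for one type of patient.

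**1. Does the ban reach the crossover patient?** Yes. Sections 4.1.1 and 7.1 both name the savolitinib + placebo arm as a form of savolitinib monotherapy, allow it up to objective progression, and prohibit it afterwards. Neither paragraph contains an exception or refers to crossover.

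**2. Does the crossover rule cover the same time?** Yes. In Section 4.1.2 and footnote i the interval runs from the assessment of PD to the addition of osimertinib. Throughout it the patient is past RECIST 1.1 progression and savolitinib is the only active drug. That is the state the ban prohibits.

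**3. Is there really an interval?** Yes. Before crossover the investigator must document PD and obtain the study physician's approval to unblind (Section 6.3), the patient must sign a separate crossover consent form (Section 4.1.2), and the ePRO questionnaires must be completed (Table 1 footnotes). The plan is to finish within 28 days of the progression scan.

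**4. When would a site feel the conflict?** Mainly from unblinding to the first crossover dose. Before unblinding, the site usually does not know that the patient is on savolitinib alone. The exception is a patient whose osimertinib/placebo tablet was already stopped.

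**5. Who is affected?**

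| Patient in the savolitinib + placebo arm | Ban in 4.1.1 and 7.1 | Instruction in 4.1.2 and footnote i | Conflict |
|---|---|---|---|
| Progresses and crosses over | Stop savolitinib | Continue savolitinib | Yes |
| Progresses, does not cross over | Stop savolitinib | Does not apply | No |
| Crosses over after a futility declaration, no PD | Not triggered | No other anti-cancer therapy before osimertinib | No |

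**6. Do the response and progression endpoints depend on it?** Protocol 9.4.3.1 and SAP 3.2.1.1.2 count response data only up to progression. For investigator assessment, the PFS event is already dated at PD, and DoR ends on the PFS date (SAP 3.2.1.1.3 and 3.2.1.1.5). No effect on ORR, DoR or PFS is claimed.

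**The case against.** The best reply is that the protocol already gives the answer. Section 4.1.2 is the dedicated crossover section and addresses exactly this interval, and Table 2 repeats it. Section 4.1.1 refers the reader to 4.1.2 when it introduces crossover, and Table 1 footnote a sends crossover patients to Table 2. A specific rule normally overrides a general one. The ban can also be read more narrowly: it sits among rules on who may stay on treatment beyond progression for clinical benefit, and a short bridge to the combination is a transition rather than continued monotherapy. For harm to follow, a site would have to run the crossover procedure while ignoring both places that describe it.

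Much of this stands. The intent is recoverable, and nothing in the documents shows that sites have stopped or would stop savolitinib. What does not stand is the conclusion that the text is adequate. The ban names the placebo arm and is unconditional. Section 7.1 cites Table 2 only for data collection and further evaluations. A categorical stop-drug rule should not need another section to override it.

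A second objection concerns hypersensitivity, and it largely succeeds. A reader might infer that the conflict exposes crossover patients to a known anaphylaxis risk. Appendix I 3.4 does not support that. Its advice to avoid interruption concerns patients with suspected hypersensitivity, its severe reactions on restart are described in some patients who had an initial hypersensitivity reaction, and its controlled-restart steps apply to toxicity interruptions in the first 6 weeks or hypersensitivity at any time. A patient who tolerated savolitinib and stopped for PD is a different case, and the protocol gives no restart risk for it.

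**Conclusion.** The inconsistency is real and stands in the current protocol text. For placebo-arm patients who cross over because of PD, the rule in 4.1.1 and 7.1 is wrong as written, and the intended rule is the one in 4.1.2 and footnote i. This is an error of wording rather than a dispute about the design.

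Its size is limited. It affects one subset of one arm, whose number is redacted. The consequence of following the ban literally is a gap without active anti-cancer treatment, followed by a savolitinib restart of unquantified risk. That consequence depends on a site preferring 7.1 to 4.1.2.

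Three stronger readings are not supported:

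- **A firm maximum number of days or missed doses.** The 28 days is something sites should achieve, not a hard cap. The time from scan to unblinding is not given, and a site may know that the patient is on savolitinib alone before unblinding. No dose count is claimed.
- **Bias in ORR, DoR or PFS.** The documents give no basis for it, for the reasons in the working.
- **A flood of important protocol deviations.** The discontinuation category in SAP Table 4 lists adverse events and non-compliance, not savolitinib after PD. The full list is in the non-compliance handling plan, which is not among the documents.

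**What to change.** Add one clause to the ban in Section 4.1.1 and the same clause to the ban in Section 7.1: *except, for patients who will cross over, between investigator-assessed PD and the start of crossover treatment, when savolitinib continues uninterrupted as described in Section 4.1.2.*

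The ban then still applies to patients who progress and do not cross over. No new restart rule is proposed, because the clause removes the interruption that would call for one.

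The cost is two clauses of text. Design, dosing, data collection and analysis stay as they are, and the change adopts an intent the protocol already states twice.

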7.1.1 Rechallenge

See guidance in [Appendix I](#) for circumstances under which a patient whose study treatment was temporarily interrupted due to an AE can restart treatment.

7.1.2 Procedures for discontinuation of study treatment

The investigator should instruct the patient to contact the site before or at the time if any study treatment is stopped. A patient that decides to discontinue study treatment(s) will always be asked about the reason(s) and the presence of any AEs. The date of last intake of study treatment(s) should be documented in the eCRF. All study treatment(s) should be returned by the patient at their next on-site study visit or unscheduled visit. Patients permanently discontinuing study treatment should be given locally available standard of care therapy, at the discretion of the investigator.

Discontinuation of study treatment(s), for any reason, does not impact on the patient's participation in the study. The patient should continue attending subsequent study visits and data collection should continue according to the study protocol. If the patient does not agree to continue in-person study visits, a modified follow-up must be arranged to ensure the collection of endpoints and safety information. This could be a telephone contact with the patient, a contact with a relative or treating physician, or information from medical records. The approach taken should be recorded in the medical records. A patient that agrees to modified follow-up is not considered to have withdrawn consent or to have withdrawn from the study.

7.1.3 Follow-up of patients post discontinuation of study intervention

As a minimum, telephone contact should be made with the patient 28 days following the discontinuation of both IPs to collect new AEs and follow up on any ongoing AEs and concomitant medications (including any subsequent cancer therapy, if appropriate). Refer to Section 8.3.3 for full details on AE recordings during follow-up.

Patients who have discontinued study intervention prior to RECIST 1.1 defined radiological progression will be followed up with tumour assessments as indicated in the SoA until RECIST 1.1-defined PD or death regardless of whether or not the patient started a subsequent anti-cancer therapy, unless they have withdrawn all consent to study related assessments.

All patients will be followed for survival until the end of the study.

Patients who decline to return to the site for evaluations should be contacted by telephone as indicated in the SoA as an alternative.

7.1.4 Follow-up for survival

Patients will be followed up for survival status as indicated in the SoA until death, withdrawal of consent, or the end of the study. Survival information may be obtained via telephone contact with the patient or the patient's family, by contact with the patient's current physician, or publicly available death registries (if available). Additional assessments to be performed at the time of survival follow-up are detailed in the SoA.

7.2 Lost to follow-up

A patient will be considered potentially lost to follow-up if he or she fails to return for scheduled visits and is unable to be contacted by the study site.

The following actions must be taken if a patient fails to return to the clinic for a required study visit:

- The site must attempt to contact the patient and reschedule the missed visit as soon as possible and counsel the patient on the importance of maintaining the assigned visit schedule.
- Before a patient is deemed lost to follow up, the investigator or designee must make every effort to regain contact with the patient or next of kin by eg, repeat telephone calls, certified letter to the patient's last known mailing address or local equivalent methods. These contact attempts should be documented in the patient's medical record.
- Efforts to reach the patient should continue until the end of the study. Should the patient be unreachable at the end of the study the patient should be considered to be lost to follow-up with unknown vital status at end of study and censored at latest follow-up contact.

